However, the prolonged presence of neutrophils in gingival tissue is not tolerated in the healthy state. For example, the failure to down regulate orchestrated neutrophil transit. Oresults in an increase in neutrophil numbers in gingival tissue and a significant increase in per iodontal bone loss. Therefore, neutrophil homing to the gingival crevice is highly regulated such that under conditions of periodontal health the appropriate amount of neutrophils are present to maintain control of dental plaque bacterial growth and yet not elicit tissue damage. Evaluation of oral and blood neutrophils during experimental gingivitis showed that people with uniquely high inflammatory response had an exaggerated polymorphonuclear neutrophil response both in the oral cavity as well as in the blood (Wellappuli 2017).

Gingivitis is a reversible inflammatory condition caused by the accumulation of dental plaque and the associated disruption of the host–microbial homeostasis. During gingivitis, the microbial community transitions from being dominated by gram-positive health-associated bacteria, such as Streptococcus species, to gram-negative periopathogens, including species of the genera Porphyromonas, Tannerella, Treponema and Prevotella. This dysbiotic shift triggers inflammatory responses, leading to tissue damage and, in some cases, progression to periodontitis. Those pathogenic bacteria also contribute to the production of volatile sulfur compounds; as a result, people with gingivitis have an increased probability of having halitosis by 3.6 times (Lee et al. 2023).

A recent study (Kerns, 2023) on human experimental gingivitis identified three distinct host response phenotypes—high, low, and slow responders—based on clinical, inflammatory, and microbial parameters:

- 1. High Responders: Rapid plaque accumulation accompanied by a significant increase in gramnegative periopathogens and elevated inflammatory markers, such as interleukin-1β (IL-1β).
- 2. Low Responders: Similar plaque accumulation to high responders but lower inflammation, suggesting a more muted host response to bacterial dysbiosis.
- 3. Slow Responders: Delayed plaque accumulation and microbial succession, with prolonged dominance of health-associated Streptococcus species. This group exhibited delayed or reduced inflammation, demonstrating a more resilient microbial community and host response.

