#### 4.3 Inclusion Criteria:

- 1) Male or female volunteers aged 18-70 years
- 2) In good general health, ASA I
- 3) No clinical signs of gingival inflammation at >90% of sites observed
- 4) Absence of Periodontal Pockets, Probing Depth (PD) < 3.0 mm on all teeth/site
- 5) Absence of Clinical Attachment Loss (CAL) = 0 mm
- 6) No periodontal disease history
- 7) Have at least 20 gradeable teeth
- 8) Non-smokers
- 9) Fluent in English
- 10) For study participants of childbearing potential, both men and women, at least one of the following birth control measures must be used: abstinence, hormonal birth control (oral, injectable, transdermal, intra-vaginal), intrauterine devices, confirmed successful vasectomy, or condoms.

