# 8.0 STATISICAL ANALYSES

Correlations between tissue and blood neutrophil subsets and standard periodontal disease parameters from oral exam will be assessed. Data will be complied in SPSS version 20. Changes in the clinical parameters of experimental gingivitis such as bleeding on probing, gingival index, plaque index and probing depths during day 0, 7, 14, 21, 28 and 35 will be compared using one-way analysis of variance (ANOVA) followed by Tukey multiple comparison.

Oral neutrophil counts as well as neutrophil subset formation during day 0, 7, 14, 21, 28 and 35 in oral rinse samples as well as blood samples will be compared using one-way analysis of variance (ANOVA) followed by Tukey multiple comparison.

Multiple sites within each study participant will be evaluated using a Gingival Bleeding Index (BOP) at baseline and 3-week post product use exams. The gingivitis bleeding scores will be averaged to provide a mean score per study participant for each exam period. Product means and standard deviations will be calculated for each time period. Analysis of Variance techniques (possibly including Analysis of Covariance using the baseline scores as the covariant) will be used to compare the difference between the two test treatments using the 95% confidence level ( $p \le 0.05$ ). The correlation of baseline to post-treatment results will be assessed graphically. If there is evidence of correlation, the baseline result will be included in the ANOVA model to adjust for baseline differences.

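### For bleeding on probing, gingival index and oral neutrophil counts, one-way ANOVA with Tukey over six visits assumes equal spread in health and disease and independent visits; early change is then hard to detect

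*Protocol*

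**What the plan says.** Section 8.0 lists "bleeding on probing, gingival index, plaque index and probing depths" and states that changes in them "during day 0, 7, 14, 21, 28 and 35 will be compared using one-way analysis of variance (ANOVA) followed by Tukey multiple comparison". The next paragraph applies the same procedure to "Oral neutrophil counts as well as neutrophil subset formation during day 0, 7, 14, 21, 28 and 35". Neither paragraph mentions a participant term, an unequal-variance version or a transformation. Because Tukey adds nothing to a comparison of only two arms, visit (or arm by visit) must be the factor.

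A third paragraph of Section 8.0 sets out a separate analysis: participant-mean BOP "at baseline and 3-week post product use exams", compared between the two treatments by ANOVA or ANCOVA "using the 95% confidence level".

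Two other places bear on spread. Inclusion criterion 3 (Section 4.3) requires "No clinical signs of gingival inflammation at >90% of sites observed". The Introduction describes high, low and slow responders to experimental gingivitis, says that neutrophil numbers rise in gingivitis, and reports that "people with uniquely high inflammatory response had an exaggerated polymorphonuclear neutrophil response both in the oral cavity".

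**The concern.** One-way ANOVA with Tukey estimates one residual variance from all visits and uses it for every pair of visits. Here the visits run from health (Day 0, after a cleaning and two weeks of hygiene) through induced disease (Days 7 to 21) and back (Days 28 and 35). If spread grows with disease, contrasts between quiet visits are judged with an error taken mostly from the inflamed visits. The same people also attend every visit, and a one-way layout cannot use that pairing.

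The contrasts hit hardest are the early ones (Day 0 v 7) and the check of whether participants are back at their starting level (Day 0 v 35). Section 3 and objective 3 in Section 2 give onset and resolution a central place.

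**Working it through.** **Nothing to reproduce.** The protocol states no SD, effect size or power, so the SDs and correlations below are assumptions shown as a range.

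**Inputs from the protocol.** Six visits (Section 8.0); 60 participants (Section 4.2), each examined at every visit (Sections 6.6 and 6.7); fewer than 10% of sites inflamed at entry (Section 4.3). A proportion confined to 0 to 0.10 has an SD of at most 0.10/2 = 0.05, or 5 points. Nothing bounds the SD at Day 21 in this way.

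**Formulas.** Pooled SE of a visit contrast = √(2·MSE/n), where MSE is the mean of the six visit variances. True SE = √((s_a² + s_b² − 2ρ·s_a·s_b)/n), where ρ is the within-person correlation. The ratio of pooled to true SE does not depend on n. Above 1 is too wide; below 1 is too narrow.

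**Assumed SDs, percentage points, Days 0, 7, 14, 21, 28, 35.**
- A (mild): 5, 7, 9, 10, 7, 5; pooled 7.4
- B (moderate): 3, 6, 10, 15, 6, 3; pooled 8.3
- C (strong): 2, 5, 12, 20, 6, 2; pooled 10.1
- D (BOP-like): 3, 8, 13, 16, 9, 4; pooled √((9+64+169+256+81+16)/6) = 9.96

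**Worked example, pattern D, Day 0 v 7.** At ρ = 0: 9.96/√((9+64)/2) = 9.96/6.04 = 1.65. At ρ = 0.7: 9.96/√((73 − 33.6)/2) = 9.96/4.44 = 2.24.

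**Ratios at ρ = 0 / 0.5 / 0.7.**

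| Pattern | Day 0 v 7 | Day 0 v 35 | Day 14 v 21 | Day 21 mean alone (any ρ) |
|---|---|---|---|---|
| A | 1.22 / 1.68 / 2.09 | 1.48 / 2.09 / 2.70 | 0.78 / 1.10 / 1.41 | 0.74 |
| B | 1.75 / 2.26 / 2.64 | 2.77 / 3.92 / 5.06 | 0.65 / 0.89 / 1.10 | 0.55 |
| C | 2.65 / 3.28 / 3.69 | 5.05 / 7.15 / 9.23 | 0.61 / 0.82 / 0.99 | 0.51 |
| D | 1.65 / 2.01 / 2.24 | 2.82 / 3.91 / 4.92 | 0.68 / 0.96 / 1.22 | 0.62 |

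Day 0 v 7 is too wide in every cell. The ρ = 0 entries (1.22 to 2.65) show variance pooling alone. The rest of the range, up to 3.69, adds the effect of ignoring the repeated measures, which by itself gives 1.41 at ρ = 0.5 and 1.83 at ρ = 0.7 when all SDs are equal.

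**Neutrophil counts.** Assume lognormal counts, ln SD 0.7, mean ratios 1, 2, 4, 4, 2, 1 and 60 values per visit. The Tukey critical value is q = 4.05, or about 2.87 per pair on the z scale.
- Raw scale: squared CV = e^0.49 − 1 = 0.632. Pooled SD = √(0.632 × (1+4+16+16+4+1)/6) = √(0.632 × 7) = 2.10. SE of a contrast = 2.10 × √(2/60) = 0.384. A doubling from 1 to 2 gives 1/0.384 = 2.60, short of 2.87. Simulated power is 37%.
- Log scale: ln 2 = 0.693, SE = 0.7 × √(2/60) = 0.128, ratio 5.4. Simulated power is 99%.
- With within-person correlation of 0.3 to 0.7, raw-scale power stays at about 37% and log-scale power stays above 99%.

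**The case against.** **Inflated false positives at the peak.** A reader might infer that comparisons among inflamed visits are anti-conservative. That needs independent visits, which the design rules out. For Day 14 v 21 in pattern D the ratio is 0.68 at ρ = 0, 0.96 at 0.5 and 1.22 at 0.7; across patterns A to C the direction reverses at ρ of about 0.40, 0.62 and 0.71. Simulated Tukey familywise error in pattern B is 10.3%, 3.2% and 1.5% at ρ = 0, 0.5 and 0.7. The objection stands: false positives for that pair arise only at low to moderate correlation. What remains is that the error bar around a peak-visit mean is too narrow whatever the correlation.

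**All four clinical measures.** A reader might extend the point to plaque and probing depth. Criterion 3 limits inflammation at entry, not plaque. Probing depth is bounded at entry but not near zero, and its spread may be equal across visits. A 0/1 plaque score can lose spread near its ceiling: with SDs of 8, 15, 12, 8, 10, 8 the Day 0 v 7 ratio at ρ = 0 is 0.87, the opposite direction. The documents do not support the variance argument there.

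**The treatment effect.** Delayed onset is a between-arm question, and a Day 0 v 7 contrast across visits does not test it. The one treatment comparison that Section 8.0 spells out, BOP at 3 weeks, does not call for pooling over the six visits and is untouched. This stands and limits the consequence.

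**Silence on scale.** A transformation could be in a statistical analysis plan that is not shown, and ANOVA is compatible with log counts. That is fair for the log-scale part. It does not answer the main point, because the protocol itself names the pooled-variance, independent-visit procedure.

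**No variances in the documents.** The Introduction says that neutrophil numbers rise and that some people respond strongly; it does not say that variance rises. Unequal spread is a plausible inference, and every size here is an assumption.

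**Conclusion.** The concern holds for BOP, GI and oral neutrophil counts. The named method makes two assumptions: independent visits, which is false by design, and equal variance across health and disease, which is implausible. Under rising-then-falling SDs and ρ from 0 to 0.7, the Day 0 v 7 standard error is about 1.2 to 3.7 times too wide and the Day 0 v 35 error is wider still, so early change and an incomplete return to the starting level are under-detected. For counts with ln SD 0.7, power for a doubling at Day 7 is about 37% raw against 99% log.

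The error for these contrasts is in the conservative direction. The analysis over visits loses sensitivity; the 3-week treatment comparison of BOP is not undermined. It is a worthwhile and inexpensive improvement to Section 8.0.

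**What to change.** In Section 8.0, replace one-way ANOVA with Tukey for BOP, GI and oral neutrophil counts by a repeated-measures mixed model. Include arm, visit and arm-by-visit as fixed effects, an unstructured covariance across visits (so that each visit has its own variance), and multiplicity-adjusted contrasts. Analyse neutrophil counts as log10 and report geometric-mean ratios.

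A participant term with one common residual variance would deal with the repeated measures but would still pool the variance. Welch ANOVA with Games-Howell would do the reverse: it allows unequal variances but still treats visits as independent. Neither is enough alone.

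The cost is wording in Section 8.0, with no new data. Neutrophil effects would be read as ratios instead of differences. More covariance parameters are estimated: six visits need 6 variances and 15 covariances, 21 in all. SPSS, which the protocol names, can fit the model.

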#### 5. TEST PRODUCTS/INTERVENTIONS

Each participant randomized to the intervention group will receive mint-flavoured SALI-10 lozenges. They will be instructed to take a lozenge twice daily after brushing by letting it dissolve in the mouth. The participants will be using the SALI-10 lozenges throughout the study.

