# 6.5 Pre-Induction Phase (Health Baseline – Study participant maintain dental hygiene at home for 14 days)

# 6.5.1 Visit 1 (t-2) Day -14

Study participants will undergo an oral hard and soft tissue exam as well as measurements of probing depth (PD), attachment level (AL), visible plaque index (VPI), gingival index (GI) and bleeding on probing (BOP) and recorded on the Oral Assessment Form (Appendix 7). The biospecimens collection will include gingival crevicular fluid (GCF), sub-gingival plaque, saliva and a saline oral rinse. All study participants will receive a prophylaxis (cleaning) which involves scaling and polishing to remove all supra- and subgingival plaque and calculus. Study participants will receive their assigned study product for use at home with directions. The participants will take two lozenges daily, one after their morning brushing and one after evening brushing. They will allow the lozenges to dissolve without biting or swallowing and avoid eating and drinking for one hour. The participants will be instructed on proper oral hygiene and will be instructed to continue their home oral hygiene in addition to use of their assigned product for 14 days (2 weeks). The participants will be instructed to return the lozenges' containers at each visit for protocol compliance check. Researchers will query participants on their use of NHPs, as well as any adverse effects they experienced.

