#### 6.5.2 Visit 2 (t-1) (Day -7)

The study participants will return the containers containing the lozenges to a member of the study team. Study participants will then undergo an oral hard and soft tissue exam as well as measurements of probing depth (PD), attachment level (AL), visible plaque index (VPI), gingival index (GI) and bleeding on probing (BOP) and recorded on the Oral Assessment Form (Appendix 7). The biospecimen collection will include gingival crevicular fluid (GCF), plaque, saliva and a saline oral rinse. Researchers will query participants on their use of NHPs, as well as any adverse effects they experienced.

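### Section 8.0 sets its between-treatment bleeding comparison at a time that does not fit the visit calendar, and its baseline could be a visit after product has started

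*Protocol*

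**What the plan says.** Section 8.0 contains one analysis that names a comparison of the two treatments. It is on BOP, averaged to one score per participant per exam, and the sites "will be evaluated using a Gingival Bleeding Index (BOP) at baseline and 3-week post product use exams". No study day or visit number is attached to either exam. The method is analysis of variance at the 5% level, "possibly including Analysis of Covariance using the baseline scores as the covariant". Whether the covariate enters depends on a graph: "If there is evidence of correlation, the baseline result will be included in the ANOVA model to adjust for baseline differences".

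The two other ANOVA paragraphs in Section 8.0 list Days 0, 7, 14, 21, 28 and 35. They name no treatment factor, though they do not exclude one.

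The calendar is in Sections 5 and 6. At Visit 1 (Day -14), "Study participants will receive their assigned study product for use at home with directions". Section 5 adds: "The participants will be using the SALI-10 lozenges throughout the study". At Visit 2 (Day -7), "The study participants will return the containers containing the lozenges to a member of the study team", so product is already in use by then. Oral hygiene stops at Visit 3 (Day 0) and resumes at Visit 6 (Day 21). The heading over Visits 1 and 2 reads "Pre-Induction Phase (Health Baseline", while Visit 3 carries the label t0. BOP is recorded at all eight visits.

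**The concern.** The stated time point and the visit schedule disagree. The design gives two weeks of product before induction begins, so time on product and time in induction differ by two weeks at every later visit. A three-week mark counted from product start falls early in induction, when gingivitis is still developing. The end of induction is a different clinical state and a different test.

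The same run-in makes the choice of baseline matter. Two of the three visits that could be called baseline come after randomised product has started. A covariate taken from either is a post-treatment measurement, and if product has begun to act by then, adjusting for it takes away part of the effect being estimated.

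At stake is the one analysis in Section 8.0 that names a comparison of the arms. As written, it can be carried out on more than one visit pair, with or without adjustment.

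**Working it through.** **Inputs.** Visit days, product start and duration of use come from Sections 5 and 6. Study length comes from Section 3, and the time point from Section 8.0.

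**Check of the clock.** Day -14 to Day 35 is (35 + 14)/7 = 7 weeks, which reproduces the length stated in Section 3. Counting from Visit 1 is therefore consistent with the protocol.

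**Weeks of product at each visit**, calculated as (day + 14)/7:

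| Visit | Day | Weeks of product | Weeks without oral hygiene |
|---|---|---|---|
| 1 | -14 | 0 | not started |
| 2 | -7 | 1 | not started |
| 3 | 0 | 2 | 0 |
| 4 | 7 | 3 | 1 |
| 5 | 14 | 4 | 2 |
| 6 | 21 | 5 | 3 |
| 7 | 28 | 6 | ended |
| 8 | 35 | 7 | ended |

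**Possible readings of the time point.**
- Three weeks after product starts: -14 + 21 = Day 7 (Visit 4), which is 7/21 = one third of the way through induction.
- Three weeks after product ends: 35 + 21 = Day 56. The last visit is Day 35, so there is no exam.
- Three weeks after induction starts: 0 + 21 = Day 21 (Visit 6), which is 5 weeks of product. This is probably what was meant, since abstinence lasts three weeks and Visit 6 is labelled t3. The clock then starts at the stop of hygiene, not at product use.

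**Possible baselines.** Day -14 has 0 weeks of product, Day -7 has 1 and Day 0 has 2. Product is handed out at Visit 1 for home use and that visit's measurements are listed first, so only Day -14 is pre-product.

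**Effect of a post-product covariate (illustration; the protocol gives no effect size or correlation).** Let d0 and d21 be the arm differences at Day 0 and Day 21, and b the covariate slope. ANCOVA on Day 0 estimates d21 - b × d0, so the share of the Day 21 effect that remains is 1 - b × (d0/d21).
- Assumed b = 0.3, d0/d21 = 0.1: 1 - 0.03 = 97%.
- Assumed b = 0.5, d0/d21 = 0.25: 1 - 0.125 = 87.5%.
- Assumed b = 0.7, d0/d21 = 0.5: 1 - 0.35 = 65%.
- If d0 = 0, nothing is lost.

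**Precision from always adjusting for Day -14.** Residual variance falls by the squared correlation: 1%, 4%, 9% or 25% at assumed correlations of 0.1, 0.2, 0.3 or 0.5. The low end is plausible, because Day -14 BOP is listed before the cleaning ("All study participants will receive a prophylaxis (cleaning) which involves scaling and polishing to remove all supra- and subgingival plaque and calculus") and precedes the 14 days of instructed hygiene.

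**The case against.** The strongest reply is that this is a slip in one sentence. Day 21 is the natural endpoint of a 21-day induction, BOP is collected at every visit, and an SAP commonly defines baseline and the covariates. Much of this stands. No data are lost, Day 21 is the likely intent, and an undefined baseline would be a minor matter by itself. The timing is different in kind, because it is stated and it conflicts with the schedule. An SAP naming Day 21 would depart from the protocol's words, and an SAP following those words could test Day 7. Baseline matters here only because two of its three candidates fall after product start.

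It is also fair to say that adjusting for Day 0 answers a legitimate but different question, namely what happens during induction given the state at its start. The protocol does not say that this is the question.

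Several stronger readings are tempting, and the documents do not support them.
- A reader might infer that the protocol plainly orders a Day 7 test. It does not: the phrase has a second literal reading, Day 56.
- A reader might infer an inflated type I error. That would require trying several visit pairs and models and keeping the smallest p-value, which is conduct the protocol does not describe. The graph-triggered covariate rule does not by itself inflate the error.
- A reader might use the entry criterion on gingival inflammation to bound the spread of Day -14 BOP. That criterion is assessed at screening and is not re-applied at Visit 1.
- A reader might take BOP to be the primary endpoint. Section 8.0 does not call it that, and the objectives list microbiome modulation first.

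**Conclusion.** The point holds as a conflict between Section 8.0 and the visit calendar. The written time point is Day 7 if counted from product start and an unscheduled Day 56 if counted from the end of use. The probable intent, Day 21, is five weeks of use, not three. The gap between the first and last of these readings is two weeks, or two thirds of the induction period. Of three possible baselines, one precedes product.

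The calendar result rests only on the protocol's visit days and on product use from Visit 1 onward. That Day 21 was intended is an inference. The loss from a Day 0 covariate (3% to 35% of the effect in the cases shown) depends wholly on assumed values and is zero if product has no effect by Day 0. No error rate should be attached to the finding.

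This should be corrected before unblinding. It is a defect of wording and pre-specification, not of data collection.

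**What to change.** Reword the BOP paragraph of Section 8.0 so that both visits are named by number and day. For example: the BOP comparison is the between-arm difference in mean BOP at Visit 6 (Day 21, end of induction), estimated by ANCOVA with Visit 1 (Day -14, pre-product) BOP always in the model. If the sponsor meant another post-treatment visit, name that one instead. Delete the wording that makes ANCOVA optional and the graphical rule for including the covariate. Report the other days as supportive.

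The cost is a change of wording and one degree of freedom. Visits 1 and 6 already record BOP, so no procedure or participant burden changes. Day -14 BOP may be only weakly related to Day 21. The case for it is that it is measured before product and cannot absorb a treatment effect, not that it will bring a large gain in precision.

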#### 2. STUDY OJECTIVES

- 1) The aim of this study is to evaluate the efficacy of S. salivarius SALI-10 in modulating the oral microbiome and preventing gingivitis, using a placebo-controlled experimental gingivitis model. Specifically, the investigators aim to:

  Microbiome Modulation:
  - Assess the ability of SALI-10 to maintain higher levels of beneficial streptococci (S. sanguinis, S. oralis, S. parasanguinis and SALI-10) during plaque accumulation.
  - Determine whether SALI-10 prevents or delays the increase of gram-negative periopathogens (Tannerella, Prevotella, and Porphyromonas) and dysbiosis.
- 2) To evalute the effects of probiotic Sali-10 intake regarding clinical parameters of periodontal health during an experimental gingivitis.
- 3) To assess differences in the onset of gingivitis, the extent of the condition, and its resolution among experimental and control groups.
- 4) To evaluate the capability to establish or increase oral colonization by *Streptococcus* salivarius SALI-10. The expected outcomes will be attributed to the effect of antimicrobial and immunomodulation metabolites (mainly, the natural product Salivaricin 10) produced by this strain present in the probiotic.
- 5) To analyze the level of sulfured compounds emitted from the oral cavity with a halimeter (Halimeter PLUS) from each study participant to assess the level of halitosis objectively, then evaluate the difference between the control and test groups as they go through the experimental gingivitis clinical trial.

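### No primary outcome or time point is named among five unranked objectives, and nothing controls error across the outcomes that could support a claim of preventing gingivitis

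*Protocol*

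**What the plan says.** Section 2 numbers five objectives. The first is "to evaluate the efficacy of S. salivarius SALI-10 in modulating the oral microbiome and preventing gingivitis". The others cover clinical parameters, oral colonization, volatile sulfur compounds and, as objective 3, "To assess differences in the onset of gingivitis, the extent of the condition, and its resolution among experimental and control groups". None is ranked.

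Section 8.0 then describes three blocks of analysis:

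- **Clinical parameters.** Changes in measures "such as bleeding on probing, gingival index, plaque index and probing depths during day 0, 7, 14, 21, 28 and 35" are to be analysed by one-way ANOVA, with Tukey's procedure afterwards. The list is open-ended, the ANOVA factor (day or group) is not stated, and no significance level is given.
- **Neutrophils.** "Oral neutrophil counts as well as neutrophil subset formation during day 0, 7, 14, 21, 28 and 35 in oral rinse samples" and in blood, by the same method, again with no factor and no level.
- **Bleeding.** A "Gingival Bleeding Index (BOP) at baseline and 3-week post product use exams", averaged per participant. ANOVA, possibly with the baseline score as covariate, "will be used to compare the difference between the two test treatments using the 95% confidence level", followed by p ≤ 0.05. Whether baseline enters the model depends on a graphical look at its correlation with the post-treatment result.

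Microbiome, colonization and halitosis outcomes have objectives but no stated test in Section 8.0.

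**The concern.** Naming the primary outcome and its time point is a protocol decision, because it fixes what the trial is asked to show. Section 8.0 does not defer it: it lists parameters, days, methods and one significance level, and leaves out the ranking. As written, nothing ties the efficacy conclusion to a particular result.

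This matters more here because allocation is carried by a two-letter code. One disclosure unblinds the whole trial (Section 6.1), and the manufacturer makes it once the study is complete (Section 6.7.3). An outcome fixed beforehand is the main protection against choosing among outcomes afterwards.

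The bleeding comparison is the nearest thing to a primary test, but it is not settled either. Its visit is unclear, its baseline visit is not named, and its covariate adjustment depends on inspecting the data.

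**Working it through.** The protocol gives no familywise error rate, effect size, standard deviation or power, so there is no planned figure to reproduce. The inputs are five objectives (Section 2), four named parameters and six days (Section 8.0), p ≤ 0.05 for BOP (Section 8.0) and 60 participants in two groups (Sections 4.2 and 6.1). Thirty per arm is an assumption, since no allocation ratio is stated.

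**1. Which visit is the 3-week exam?** Product is first dispensed on Day -14 (Section 6.5.1). Three weeks of use gives -14 + 21 = Day 7 (Visit 4). Three weeks without oral hygiene ends on Day 21 (Visit 6, Section 6.7.1). Section 8.0 does not choose between them.

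**2. Chance of at least one false positive.** For k independent tests at 0.05 with no true effect, this is 1 - 0.95^k.

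| Reading | k | Result |
|---|---|---|
| Four parameters at one visit | 4 | 1 - 0.95^4 = 18.5% |
| One test per objective | 5 | 1 - 0.95^5 = 22.6% |
| All parameter-by-day cells between arms (4 × 6) | 24 | 1 - 0.95^24 = 70.8% |
| The same with Day 0 taken as baseline (4 × 5) | 20 | 1 - 0.95^20 = 64.2% |

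**3. Allowing for correlation.** The 24 cells were simulated as two-sided z-tests (400,000 draws), with an assumed equal correlation between parameters and between days. The result is 64% at correlation 0.3, 53% at 0.5, 38% at 0.7 and 29% at 0.8. With 20 cells it is 48% at 0.5 and 27% at 0.8. Positive correlation would also lower the 18.5% and 22.6%, but they stay above 5% unless the tests are perfectly correlated.

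**4. The day-factor reading.** If the ANOVA factor is day and Tukey holds each parameter at 0.05, there are four families, giving 18.5% if independent. Adding neutrophil counts and subsets, each in rinse and blood, makes 4 + 2 × 2 = 8 families: 1 - 0.95^8 = 33.7%. These are changes over time, not treatment tests, so they cannot answer objectives 3 and 5, which compare the two groups.

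**5. What one primary test buys.** With 30 per arm and a normal approximation, the difference detectable with 80% power is (1.960 + 0.842) × √(2/30) = 0.72 SD at alpha 0.05. Bonferroni over 24 cells gives alpha 0.05/24 = 0.0021. The detectable difference rises to 1.01 SD, and power at 0.72 SD falls from 80% to 39%.

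**The case against.** A reader might infer that 24 comparisons share p ≤ 0.05, so that the trial carries a false-positive rate of up to 71%. The document does not support this. The 0.05 level is written once, for BOP. The 24 cells are assigned to one-way ANOVA with Tukey. With two groups Tukey adds nothing, so the factor is plausibly day, with control inside each ANOVA. Separate between-arm tests of every cell are one reading of an ambiguous sentence. The 71% also assumes independence, which is unlikely: a gingival index score of 2 includes bleeding on probing (Section 7.4), and days repeat within participants.

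A reader might also infer that any one significant test counts as success. The protocol states no success rule of any kind; the defect is its absence. Nor are chemokines among the objectives: they appear only as a laboratory assay (Section 7.5). Detailed multiplicity adjustment may properly sit in a statistical analysis plan that is not shown, and some pages were removed from the text, so the absence of a primary outcome is established only for what is visible.

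All of that stands. It does not remove the core. Objectives 3 and 5 require between-arm comparisons on several outcomes, Tukey controls nothing across parameters or objectives, and the BOP test is neither labelled primary nor tied to one clear visit.

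**Conclusion.** The concern holds in this limited form: the visible protocol designates no primary outcome or time point, provides no error control across outcomes, and does not say which result supports the preventive claim. If more than one result may support it, the false-positive rate for that claim is above 5%. It is about 19% for four independent parameters at one visit and about 23% for one independent test per objective. Roughly 30% to 70% applies only if all 24 cells were tested between arms at 0.05, and depends on the assumed correlation (0.8 down to zero). The detectable differences rest on 30 per arm. This should be corrected, and it can be corrected fully before the code is revealed.

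**What to change.** Before the A/B code is revealed, amend Sections 2 and 8.0 to name one primary outcome, one visit and one between-arm contrast. A workable example is participant-mean BOP at Day 21, compared between arms by ANCOVA at two-sided 0.05 with the Day -14 value as a fixed covariate.

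- The sponsor must confirm that Day 21 is the intended 3-week exam, and state the visit by day number.
- Day -14 is preferable as covariate because it precedes product use. Day 0 follows two weeks on product, and adjusting for it could remove part of a treatment effect.
- The fixed covariate replaces the decision based on a graph.
- Label the remaining clinical parameters and days secondary. Label the microbiome, chemokine, neutrophil and sulfur-compound outcomes exploratory. Report both groups with confidence intervals and no efficacy claim.
- State the ANOVA factor for the clinical and neutrophil blocks.

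The cost is an amendment of wording, with no new data, visits or participants. The downside is that a positive result on another outcome alone would no longer support the efficacy claim.
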